8.2.1 Sample size justification

No formal sample size calculation has been performed for this study. The sample size required for the trial is at least 40 randomized paediatrics subjects recruited from sites within the European Union and Canada. This sample size is considered adequate to achieve the study objectives and provide sufficient information to evaluate data descriptively.

8.3 Secondary effectiveness analysis

The following secondary effectiveness endpoints will be summarized descriptively by treatment group for the FAS:

- Proportion of subjects achieving hemostatic success at 4 minutes following randomization and no bleeding requiring treatment at the TBS occurs any time prior to final fascial closure;
- Proportion of subjects achieving hemostatic success at 10 minutes following randomization and no bleeding requiring treatment at the TBS occurs any time prior to final fascial closure;
- Proportion of subjects with no re-bleeding at the TBS.

Two-sided 95% CIs for the proportions of subjects with hemostasis at 4 minutes and 10 minutes will be constructed for each treatment group separately (P_E for EVARREST and P_C for Control), using the Clopper-Pearson method. In addition, for each time point, a two-sided 95% CI will be reported for the ratio proportion of successes (hemostasis achieved) in the EVARREST group/proportion of successes in Control group (P_E/P_C), using the Farrington-Manning score method.

8.4 Analysis of follow-up data

The following follow-up data will be summarized descriptively for post-surgery to hospital discharge (within 72 hours prior to discharge) and for 30-day (± 14 days) visit:

- Re-hospitalizations, surgical procedures, and transfusions since hospital discharge [for 30-day (± 14 days) visit only];
- Relevant changes in medical history since screening;
- Presence of clinically significant changes to subject since baseline;
- Presence and duration of subject presence in elevated care unit (ICU, step-down unit, etc.);
- Presence and duration of subject being on ventilator post-operatively;
- Laboratory data (full blood count with white blood cell differential, and coagulation parameters) (only for post-surgery to hospital discharge - within 72 hours prior to discharge).

8.5 Statistical/analytical issues

8.5.1 Handling of dropouts or missing data

It is not anticipated that there will be any data missing for treated subjects for the primary endpoint, but if there is, missing data will not be imputed for the primary effectiveness analysis.

Analyses of binary secondary endpoints will consider missing data as failures; missing data for other secondary endpoints will not be imputed.

If there are incomplete dates and calculations (e.g. time since procedure) are needed, the following rules are used (no rules will be applied for missing years; this data would normally be expected to be queried):

- Missing date which includes the procedure date: the rules below are followed unless the derived date is pre-procedure, when the derived date will be 1 day after the procedure.
- Missing day: 15th used

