8.6 Handling of Missing Data

It is not anticipated that there will be any data missing for treated subjects for the primary endpoint, but if there is, missing data will not be imputed for the primary analysis.

Analyses of secondary endpoints will consider missing data as failures.

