5. ANALYSIS SETS

The following three analysis sets defined:

- The Full Analysis Set (FAS) consists of all randomized subjects (equivalent to the Intent-to-Treat [ITT] set). Subjects who do not complete the procedure with the use of EVARREST or SURGICEL after randomization will be included in the FAS analysis;
- The Per-Protocol (PP) analysis set (Evaluable set) consists of all FAS subjects who have no major protocol deviations affecting the primary effectiveness endpoint and have data available for this endpoint;
- The Safety analysis set consists of all subjects who received treatment.

Major protocol deviations will be determined prior to database lock.

The primary effectiveness endpoint will be analyzed using the FAS and the PP set. However, the primary analysis will be based on the FAS. The PP analysis will be considered supportive.

All secondary effectiveness endpoints (listed in section 8.3) will be analyzed using the FAS set, while safety endpoints (listed in section 9) will be analyzed using the Safety set.

If any patients are mis-randomized (randomized to one treatment, but received the other), then data for the FAS will be summarized ‘as randomized’, and data for the safety set will be summarized ‘as treated’.

If more than 2 patients are mis-randomized, then additional analyses for the FAS will be performed, with patients allocated to treatment groups ‘as treated’. Patients who are mis-randomized will be considered major protocol deviations.

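### A randomised child with no recorded time to haemostasis leaves the primary FAS median and its confidence interval; a worst-rank rule would keep that child in

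*SAP*

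**What the plan says.** SAP section 5 bases the primary analysis on the FAS, which it equates with intention to treat, and adds: "Subjects who do not complete the procedure with the use of EVARREST or SURGICEL after randomization will be included in the FAS analysis". The PP set, which is supportive, is the only set that formally requires primary endpoint data.

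SAP 8.5.1 opens with "It is not anticipated that there will be any data missing for treated subjects for the primary endpoint" and continues "but if there is, missing data will not be imputed for the primary effectiveness analysis". Protocol 8.6 has the same rule: "missing data will not be imputed for the primary analysis". Both statements of expectation concern treated subjects; neither covers children randomised but not treated. For the 4- and 10-minute endpoints, SAP 8.5.1 goes the other way: "Analyses of binary secondary endpoints will consider missing data as failures".

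SAP 8.2 defines the endpoint as the time from randomisation to the last detectable bleeding at the target site. The planned statistics are descriptive summaries and a 95% distribution-free interval for the median in each arm. No ceiling, censoring time or worst-rank rule is given. SAP 10.2.1 mentions a sensitivity analysis summary in the title of in-text table T3, but SAP section 8 defines no such analysis.

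Two provisions limit the problem. The protocol synopsis (Procedure) requires the time to be recorded for all subjects whether or not they had further treatment. SAP 10.2 has tables of continuous data show the number of missing observations.

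**The concern.** A blank time cannot enter a mean, a median or an order-statistic interval. The child stays in the FAS count, but the primary result becomes a complete-case result. A time with no recorded end is unlikely to belong to a child who stopped bleeding quickly, so the loss would tend to come from the slow end of the distribution and shorten that arm's median.

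The planned supporting analyses would not show this. Table T3 draws on Table 14.2.1.1 (FAS) and Table 14.2.1.2 (PP), and both omit the child. Meanwhile the binary endpoints keep every randomised child in the denominator, so two sets of tables labelled FAS could rest on different children.

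**Working it through.** The plan states no power, effect size or expected dropout, so there is no figure of its own to reproduce. The check is what the rule does to the planned statistics.

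**Inputs.** At least 40 children randomised 1:1 (SAP section 2), so 40/2 = 20 per arm is assumed. The interval is 95% distribution-free (SAP 8.2). The SAP does not say how the ranks are chosen, so I take the narrowest symmetric pair with at least 95% coverage.

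**Order statistics.** For n observed times, the interval from the l-th to the (n+1−l)-th ordered time has coverage 1 − 2·P(X ≤ l−1), with X ~ Binomial(n, 0.5). For n = 20 and l = 6: 1 − 2 × 21,700/1,048,576 = 95.9%. If the k slowest children have no time and are dropped, n = 20 − k and the median sits at rank (n+1)/2.

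| Slowest children dropped | n | Median at rank | 95% limits at ranks | Coverage |
|---|---|---|---|---|
| 0 | 20 | 10.5 | 6 and 15 | 95.9% |
| 1 | 19 | 10 | 5 and 15 | 98.1% |
| 2 | 18 | 9.5 | 5 and 14 | 96.9% |
| 3 | 17 | 9 | 5 and 13 | 95.1% |
| 4 | 16 | 8.5 | 4 and 13 | 97.9% |

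If those children are instead kept at the worst rank, n stays 20, the median stays at rank 10.5 and the limits stay at the 6th and 15th times. Both limits remain observed times for up to five such children, since 20 − 5 = 15.

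**Illustration in minutes (assumption).** Protocol section 1 gives pooled control rates of 49.4% with haemostasis at 3 or 4 minutes and 78.3% at 10 minutes. Treat the first as a 4-minute rate and fit a lognormal:

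- σ = ln(10/4) / (z(0.783) − z(0.494)) = 1.149, and the median is 4.07 min.
- With k dropped, the complete-case median sits at percentile (20 − k)/40 of the full distribution.
- k = 1: 47.5th percentile, about 3.8 min. k = 2: 45th percentile, about 3.5 min.

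A second shape, piecewise exponential through the same two rates with 10,000 simulated arms of 20, agrees. The typical control median is 4.12 min with none lost. It is 3.76 min if a quarter of the children still bleeding at 10 minutes lack a time (0.25 × 4.34 ≈ 1.1 on average), and 3.51 min if half do (about 2.2). The typical upper limit goes from 8.2 to 7.7 and 7.0 min. Kept at the worst rank, the median stays at about 4.1 min and the upper limit at about 8.2 min.

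**Direction.** On the same pooled rates, the expected number without haemostasis at 10 minutes is 20 × (1 − 0.783) = 4.3 in control and 20 × (1 − 0.97) = 0.6 on EVARREST. Even if every such EVARREST child lacked a time, the simulated EVARREST median would move only from 1.21 to 1.15 min.

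**The case against.** The strongest reply is that the protocol already guards against this. A child who fails the assigned product and is rescued should still have a time recorded, and that time will be long. Severe bleeding is excluded, and haemostasis is also assessed when final closure begins. Any loss would show in the missing counts and subject listings. The trial is descriptive, with a separate interval per arm and no planned test of the primary endpoint. All of this stands. It makes the likely number of affected children small, but it does not supply a rule for a child whose end of bleeding nobody observed, and showing a missing count does not repair the median.

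A reader might infer three stronger things that the documents do not support:

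- **That treatment failures as a class leave the primary analysis.** The recording requirement keeps them in. The gap is limited to children with no observed end of bleeding, for example randomised but untreated, or procedure abandoned.
- **That the same child always counts as a failure at 4 and 10 minutes.** That follows only if those assessments are also missing or failed. A child recorded as a success at those times, with no later bleeding needing treatment but no absolute time, is a success there and missing in the primary.
- **That the control median could plausibly fall to about 3 min.** That is the four-dropped case. With 4.3 of 20 controls expected to lack haemostasis at 10 minutes, nearly all of them would have to lack a time.

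The rates behind the minutes are also a weak guide. They pool six earlier studies, four described as adult, and include severe bleeding and cardiovascular surgery with comparators other than SURGICEL.

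**Conclusion.** The point holds in a narrow form. The stated rule turns the primary FAS analysis into a complete-case analysis for any randomised child whose end of bleeding was not observed, and no other planned analysis brings that child back.

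The size in ranks is exact, given 20 per arm and that the lost children are the slowest: half a rank off the median per child, with no change in the upper limit for one loss and a fall to the 14th, 13th and 13th ordered times for two, three and four. The minutes are illustrative only. The documents do not say how many children will lack a time; the number is probably small, and at zero the rule does nothing.

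The distortion would favour the arm with more such children, probably SURGICEL, and so would tend to work against EVARREST. It is worth correcting because the planned statistics depend only on ranks, so a better rule requires no invented value.

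**What to change.** In SAP 8.2 and 8.5.1, state that:

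- Any FAS subject without observed haemostasis at the target site is treated as longer than every observed time when the median and its distribution-free interval are computed. Censoring at the last observation is an alternative. It gives the same median when that observation is later than the ordered times in use, but an early censoring time would need a censored-data method.
- A child seen to reach haemostasis but with no exact time recorded is not worst-ranked. That time is taken to lie between the last assessment with bleeding and the first without.
- A child whose bleeding stopped before any product was applied keeps the observed time.
- The observed-only mean, SD and median are shown beside the result, with the number of children they exclude.

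Define the sensitivity analysis named for table T3 in SAP 10.2.1 to match. Write the rule before anyone has seen which children lack a time.

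The cost is a few sentences and one extra row in Table 14.2.1.1. An arm's reported median may become longer, and with six or more such children among 20 the upper limit would be reported as not reached.

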8.5.2 Interim analyses and data monitoring

No interim analysis will be performed for this study.

8.5.3 Multiple comparison / multiplicity

Not applicable.

9. SAFETY EVALUATION

9.1 Adverse events

The following safety/secondary endpoints will be descriptively summarized using the Safety set:

- Proportion of subjects with adverse events that are potentially related to bleeding at the TBS;
- Proportion of subjects with adverse events that are potentially related to thrombotic events;
- Proportion of subjects with re-treatment at the TBS;
- Incidence of adverse events;
- Hemoglobin, Hematocrit, and Platelets, at screening, baseline, and post-surgery to hospital discharge (within 72 hours prior to discharge);
- Estimated intra-operative blood loss;
- Volume of blood and blood products transfusions (red blood cells, whole blood, fresh frozen plasma, platelets, and cryoprecipitates), intra-operatively, prior to hospital discharge, and after discharge.

9.2 Clinical laboratory evaluation

Blood samples will be taken for full blood count with white blood cell differential, and coagulation parameters, at screening, baseline, and post-surgery to hospital discharge (within 72 hours prior to discharge).

9.3 Vital signs, physical findings and other observations related to safety

Vital signs will not be collected in this study. A physical exam will be performed and medical/surgical history data will be collected at screening. In addition, a physical exam will be performed post-surgery to hospital discharge (within 72 hours prior to discharge).

9.4 Methods of analysis

All safety variables will be summarized descriptively only, for Safety analysis set. No inferential statistical analysis will be carried out.

Adverse events will be summarized descriptively by the treatment received, using Medical Dictionary for Regulatory Activities (MedDRA) terminology, in SI units. Values and changes from baseline will be listed, but not summarized.

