8.4.2 Methods of Analysis

Adverse events will be summarized descriptively by the treatment received, using Medical Dictionary for Regulatory Activities (MedDRA) terminology.

Laboratory values (including coagulation parameters) will be reported in International System (SI) units. Values and changes from baseline will be listed and summarized. Clinically significant changes will be reported as part of the AE summary.

AEs (MedDRA terminology) will also be summarized into Infants and toddlers (28 days to 23 months), Children (2 to 11 years) and Adolescent (12 to <18 years).

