4. CHANGES IN THE CONDUCT OF THE STUDY OR PLANNED ANALYSIS

Not applicable.

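### The SAP reverses the protocol's planned summary of laboratory changes from baseline and names no adverse-event summary by age group, and declares neither departure

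*SAP*

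**What the plan says.** **Protocol 8.4.2** sets three requirements beyond a summary of adverse events by treatment received:

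- On laboratory values, reported in SI units: "Values and changes from baseline will be listed and summarized".
- On important laboratory changes: "Clinically significant changes will be reported as part of the AE summary".
- On age: "AEs (MedDRA terminology) will also be summarized into Infants and toddlers (28 days to 23 months), Children (2 to 11 years) and Adolescent", the last group being those aged 12 to under 18 years.

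Protocol section 8 adds that the SAP is to build on and add to the analysis described there.

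**SAP 9.4** opens with "All safety variables will be summarized descriptively only, for Safety analysis set". It continues with "Adverse events will be summarized descriptively by the treatment received", coded in MedDRA, and then says "Values and changes from baseline will be listed, but not summarized". It does not mention age.

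**SAP section 4**, on changes in conduct or planned analysis, reads "Not applicable".

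**The concern.** The laboratory sentences in the two documents are almost word for word the same, but they give opposite instructions on summarising. The age-group summary of adverse events is in the protocol and is not visible in the SAP. Because section 4 declares no change, a reader of the SAP alone would not know that either item had been dropped.

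Safety is a named objective, and the population runs from 28 days to under 18 years. If the SAP is followed as written, anyone wanting adverse events by age group, or laboratory change by arm, would have to rebuild them from per-subject listings. The programmer also gets no guidance on which of the SAP's conflicting laboratory statements governs.

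**Working it through.** There is no stated figure to reproduce. The check compares the texts and counts the planned outputs.

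**1. Laboratory changes from baseline.** The SAP 9.4 sentence has lost its subject: it follows a sentence that puts adverse events in SI units. The match with protocol 8.4.2 shows that laboratory values are meant. On values, the SAP contradicts itself:

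| Place in SAP | Treatment of laboratory data |
|---|---|
| 9.4, first sentence | "All safety variables will be summarized descriptively only, for Safety analysis set" |
| 8.4, whose list includes laboratory data | "The following follow-up data will be summarized descriptively for post-surgery to hospital discharge" |
| 9.1 | Haemoglobin, haematocrit and platelets summarised at screening, baseline and before discharge |
| Tables 14.3.2.1 to 14.3.2.3 | Values tabulated at the same three time points |
| 9.4, last sentence | "Values and changes from baseline will be listed, but not summarized" |

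So values probably will be summarised, and the clear loss is the summary of changes. Laboratory tables naming a change from baseline in title or notes: 0 of 3. Listings 16.2.7.2.1 to 16.2.7.2.3 naming a derived change: 0 of 3, although other listings, such as the adverse-event listing, do state their derived variables. The listing of changes that SAP 9.4 promises is therefore not assigned to any output by title or note.

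**2. Definition of baseline.** Footnote 3 of the protocol's schedule of events and protocol 7.1.1 use the pre-operative result nearest to surgery. Protocol 7.1.2 adds that, when tests are repeated, only that result is collected. Section 7.1.1 requires only one pre-operative laboratory evaluation, at any time within 21 days before surgery. The SAP shows screening and baseline as separate time points and does not restate the rule. A child tested only at screening could then have no value under baseline, and so no change.

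**3. Adverse events by age.** Adverse-event tables naming age in title or notes: 0 of 6 (14.3.1.1 to 14.3.1.6). The general rule in SAP 10.2 is tabulation by treatment group and, where suitable, by visit. By contrast, SAP 8.2 and the note to Table 2.1 apply the same three age groups to the primary endpoint, which covers Tables 14.2.1.1 and 14.2.1.2. The split was carried over for effectiveness and not for safety.

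**4. What would be missing.**

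- Adverse events: 3 age groups × 2 arms = 6 columns.
- Laboratory change: 6 named parameters (haemoglobin, haematocrit, platelets, PT, aPTT, INR) × 2 arms = 12 summaries at least.

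**5. What an age table could show.** The documents do not give the size of the 28 days to 23 months group: it includes the 4 planned infants under 1 year plus any 1-year-olds among the first 36 subjects. The group size n is therefore an assumption. With zero events in n subjects, the exact two-sided 95% upper limit is 1 − 0.025^(1/n):

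| Assumed n | Upper limit |
|---|---|
| 4 | 60.2% |
| 6 | 45.9% |
| 8 | 36.9% |
| 10 | 30.8% |

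These tables can describe what happened in the youngest children. They cannot exclude even common events.

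**The case against.** The strongest counter-argument is that this is an alignment point in a descriptive study of about 40 children, and that the missing outputs are inferred from titles and notes. Layout is in table shells AS, AM and L, in a separate attachment, and the first three adverse-event tables have empty notes. On age, the SAP is only silent. Since it supplements the protocol, silence does not withdraw the requirement. On laboratory data, a self-contradictory SAP does not settle what will be produced.

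Much of this is fair. A split or change column in the shells cannot be excluded, nor can a declaration in the opening SAP pages, which were also unavailable; the visible change notes concern analysis sets only. The age item is an omission, whereas the laboratory item is a contradiction. But a shell would not cure an explicit instruction not to summarise, or a section 4 that declares nothing. Silence does not produce a table either, when the same split is written out for the primary endpoint.

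Three further points stand:

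- Enrolment is staged at 1 year, so the three adverse-event age groups would not isolate the staged infant cohort. The case rests on the protocol's own requirement, not on the staging.
- The count of 6 columns assumes age crossed with arm, which the age sentence in protocol 8.4.2 does not itself state.
- There is real mitigation. Per-subject listings hold each child's events and laboratory values, and clinically significant laboratory changes go to the adverse-event summary under the protocol. Table 14.2.4 reports whether clinically significant changes since baseline occurred, though their scope is not defined.

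**Conclusion.** The concern holds. SAP 9.4 reverses a protocol-specified summary of laboratory change. Neither SAP 9.4 nor the title or notes of any adverse-event table provides the protocol's summary by three age groups, and section 4 declares neither departure. The conclusion is limited to the SAP text and the table and listing titles and notes, and assumes that the unseen shells do not supply what is missing.

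The consequence is incomplete and internally inconsistent safety reporting. The primary endpoint analysis is unaffected, no planned inference depends on this, and the raw data remain available in listings.

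**What to change.** 1. In SAP 9.4 and 10.2.2, add descriptive MedDRA tables by system organ class and preferred term, with overall adverse-event and serious adverse-event counts, by treatment received and the three protocol age groups.
2. Correct SAP 9.4 to say that laboratory values, in SI units, and their changes from baseline are both listed and summarised. Define baseline by the protocol's rule, the pre-operative result nearest to surgery. Add baseline and change columns to Tables 14.3.2.1 to 14.3.2.3 and a derived change to Listings 16.2.7.2.1 to 16.2.7.2.3.
3. If either departure is intended, state and justify it in SAP section 4 instead.

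If the shells already contain the age split or the change columns, the titles, notes and SAP 9.4 need only be brought into line with them.

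The cost is SAP wording and a few tables or columns from data already collected, with no new procedures. The one drawback is small cells in the youngest group, so the age tables should be labelled as descriptive only.
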